the event or the date of last documented follow-up since randomization for those who are censored. Date of last documented follow-up since randomization is the maximum value among the dates of randomization, randomization programming, any study scheduled follow-up visit, exit, adverse event onset, adverse event resolved, system modification, and healthcare utilization. Rand is an indicator variable for randomized treatment groups (1=aCRT ON, 0=aCRT OFF).

The hazard ratio for treatment arm (aCRT ON) versus control arm (aCRT OFF) will be reported with its associated p-value and 95% confidence interval. The null hypothesis will be rejected when the p-value is below the critical value for the (interim or final) analysis. The actual cumulative α level will be calculated based on the actual number of primary events included in each interim analysis. The estimated cumulative α -level is approximately 0.00002, 0.00304, 0.0193 and 0.05 at the 1st interim with 275 events, 2nd interim with 550 events, 3rd interim with 825 events and the final analysis with 1100 events, respectively (see details in section 0). It will be concluded that aCRT reduces the incidence of the primary endpoint when the null-hypothesis is rejected and the hazard ratio is below 1. Kaplan-Meier plots for incidence of primary endpoint will be presented by treatment arms, for all patients and for the separate NYHA class groups. The absolute event rate difference at 2 years post randomization will also be calculated.

The following model assumptions will be checked:

1. Proportional hazards between treatment arms: an interaction term of treatment arm by time (in log scale) will be added into the model (see the code below). If this interaction effect is not significant, the proportional hazard assumption holds. Otherwise, this interaction term should be kept in the model as a remedy for non-proportional hazards, and any secondary analysis where treatment (or treatment by subgroup factor interaction) is included should also include the corresponding interaction term with time. Being time dependent, the treatment effect will be assessed every 6 months to the end of the follow-up to monitor the direction. Significance of the treatment effect will be based on its estimate at 24 months using a contrast.

```
PROC PHREG DATA=primary;  
  CLASS NYHA site;  
  MODEL time*event(0) = rand rand_t / TIES=efron;  
  rand_t = rand*log(time);  
  STRATA NYHA;  
  RANDOM site/ dist = gamma;  
RUN;
```

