4.3.4 Sensitivity Analyses: LBBB Determination and aCRT Programming

As indicated in section **Error! Reference source not found.**, two sensitivity analyses will be performed for the primary objective. One is an ITT analysis of the randomized patients whose LBBB is confirmed by the ECG Core Lab. The purpose of this sensitivity analysis is to verify the effect of aCRT on the incidence of HF events or death among the true LBBB patients and to assess the impact of LBBB misclassification on the results. This analysis will be conducted in a similar way to that of the primary analysis:

```
PROC PHREG DATA=LBBB;  
CLASS NYHA site;  
MODEL time*event(0) = rand / TIES=efron;  
STRATA NYHA;  
RANDOM site/ dist = gamma;  
RUN;
```

Here, 'event', 'time' and 'aCRT' are defined in the same way as those in the primary analysis. A p-value for treatment below the cumulative α -level of approximately 0.00002, 0.00304, 0.0193 and 0.05 at the 1st, 2nd, 3rd interim and the final analysis, respectively, is significant.

The other sensitivity analysis will also be conducted in the randomized patients with ECG Core Lab confirmed LBBB, while the purpose is to verify the effect of aCRT on the primary endpoint based on the actual aCRT programming over time. Given this being said, this analysis will not follow the ITT principle and:

- Patients with major eligibility violations will be excluded (also when the violation becomes apparent only after randomization).
- Patients with major protocol violations after randomization, such as being programmed permanently to a mode that deviated from original randomization assignment due to a system modification after randomization, will be censored at the time of protocol violations.
- Patients' actual aCRT programming will be a time-varying covariate that has 3 categories: ACRT ON, ACRT OFF, and Neither, counting from the time randomization programming is implemented.

This analysis will be conducted using the following SAS PHREG procedure:

```
PROC PHREG DATA=LBBBCross COVSANDWICH (AGGREGATE) ;  
  ID pt;  
  CLASS NYHA site pt;  
  MODEL (start,stop)*event(0) = aCRTprog / TIES=efron;  
  STRATA NYHA;  
RUN;
```

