where aCRTprog indicates patients' actual aCRT programming. Patients whose actual aCRT programming change over time get multiple records in the input dataset. Whenever there is a change, for instance, there will be one record in the randomized arm up until time of crossover and another record from time of crossover until the time that a primary endpoint is met or the time of censoring without meeting a primary endpoint. The COVSANDWICH option ensures the model accounts for multiple records coming from the same patient. In order to implement the COVSANDWICH option in SAS, random site effect will not be considered in this sensitivity analysis. A p-value for treatment below the cumulative α -level of approximately 0.00002, 0.00304, 0.0193 and 0.05 at the 1st, 2nd, 3rd interim and the final analysis, respectively, is significant.

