Sensitivity Analyses: LBBB Determination and aCRT Programming

The first sensitivity analysis is to verify the effect of aCRT treatment on all-cause mortality among the true LBBB patients. The same model used in the primary analysis will be used in this sensitivity analysis. The only difference is that patients included in the sensitivity analysis must have their LBBB confirmed by ECG Core Lab.

```
PROC PHREG DATA=mortality_LBBB;  
  CLASS NYHA site;  
  MODEL time*death(0) = rand / TIES=efron;  
  STRATA NYHA;  
  RANDOM site/dist = gamma;  
RUN;
```

The second sensitivity analysis is to check the effect of aCRT on all-cause mortality based on the actual aCRT programming, given that patients' LBBB has been confirmed by the ECG Core Lab. Again, actual aCRT programming will be a time-varying covariate, meaning patients whose actual aCRT programming change over time will have multiple records in the input dataset. This will be performed using the COVSANDWICH option in the SAS PHREG procedure, and random site effect will not be considered in this sensitivity analysis.

```
PROC PHREG DATA=mortality_LBBBCross COVSANDWICH (AGGREGATE);  
  ID pt;  
  CLASS NYHA site pt;  
  MODEL (start,stop)*death(0) = rand / TIES=efron;  
  STRATA NYHA;  
RUN;
```

Subgroup Analysis: Interaction with Treatment

Same as for the primary endpoint, the subgroups to be considered for all-cause mortality include:

- Geography: US/Canada vs. International
- Age
- Gender: Males vs. Females
- QRS duration: ≤ 150 ms vs. > 150 ms
- AV conduction time: median as cutoff
- LBBB: Core Lab confirmed vs. Core Lab not confirmed
- NYHA class (in different model where NYHA class is a covariate not a stratification factor)
- HF etiology
- Renal dysfunction
- Diabetes

The effects of treatment by subgroup interaction on all-cause mortality will be evaluated using codes similar to:

```
PROC PHREG DATA=mortality_Subgroup;  
  CLASS NYHA site Subgroup;  
  MODEL time*death(0) = rand subgroup rand*subgroup / TIES=efron;  
  STRATA NYHA;  
  RANDOM site/dist = gamma;  
RUN;
```

Ancillary Analysis: Covariate Adjustment

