The first sensitivity analysis is to verify the effect of aCRT treatment on HF event among the true LBBB patients. The same model used in the primary analysis will be used in this sensitivity analysis. The only difference is that patients included in the sensitivity analysis must have their LBBB confirmed by ECG Core Lab.

```
PROC PHREG DATA=HFevent_LBBB;  
  CLASS NYHA site;  
  MODEL time*HFevent(0) = rand / TIES=efron;  
  STRATA NYHA;  
  RANDOM site/dist = gamma;  
RUN;
```

The second sensitivity analysis is to check the effect of aCRT on HF event based on the actual aCRT programming, given that patients' LBBB has been confirmed by the ECG Core Lab. Again, actual aCRT programming will be a time-varying covariate, meaning patients whose actual aCRT programming change over time will have multiple records in the input dataset. This will be performed using the COVSANDWICH option in the SAS PHREG procedure, and random site effect will not be considered in this sensitivity analysis.

```
PROC PHREG DATA=HFevent_LBBBCross COVSANDWICH (AGGREGATE);  
  ID pt;  
  CLASS NYHA site pt;  
  MODEL (start,stop)*HFevent(0) = rand / TIES=efron;  
  STRATA NYHA;  
RUN;
```

Subgroup Analysis: Interaction with Treatment

The same subgroups that are considered for the primary endpoint and 1st secondary endpoint will be considered for intervention for heart failure decompensation. These include:

- Geography: US/Canada vs. International
- Age
- Gender: Males vs. Females
- QRS duration: ≤150ms vs. >150ms
- AV conduction time: median as cutoff
- LBBB: Core Lab confirmed vs. Core Lab not confirmed

- NYHA class (in different model where NYHA class is a covariate not a stratification factor)
- HF etiology
- Renal dysfunction
- Diabetes

The effects of treatment by subgroup interaction on intervention for heart failure decompensation will be evaluated using codes similar to:

```
PROC PHREG DATA=HFevent_Subgroup;  
  CLASS NYHA site Subgroup;  
  MODEL time*HFevent(0) = rand subgroup rand*subgroup / TIES=efron;  
  STRATA NYHA;  
  RANDOM site/dist = gamma;  
RUN;
```

Ancillary Analysis: Covariate Adjustment

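### The as-treated code for mortality and HF events fits the randomised arm (`rand`) instead of actual programming, and the primary-endpoint version leaves the three-category `aCRTprog` out of CLASS

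*SAP*

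**What the plan says.** The SAP plans two sensitivity analyses in patients whose LBBB the ECG Core Lab confirms: one by randomised arm and one by the programming actually in force. Section 4.1.2.3 sets these out for the primary objective; 4.4.1 and 4.4.2 repeat them for mortality and HF events.

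- **Primary endpoint, 4.3.4.** The as-treated covariate has three categories (ON, OFF, Neither) and follow-up is split when programming changes. The code is introduced with "This analysis will be conducted using the following SAS PHREG procedure" and fits "MODEL (start,stop)*event(0) = aCRTprog / TIES=efron", "where aCRTprog indicates patients' actual aCRT programming". Its class line is "CLASS NYHA site pt".
- **Mortality, 4.4.1.** The text says "actual aCRT programming will be a time-varying covariate", with several records for a patient whose programming changes. The code is "MODEL (start,stop)*death(0) = rand / TIES=efron".
- **HF events, 4.4.2.** The description is the same. The code is "MODEL (start,stop)*HFevent(0) = rand / TIES=efron".

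`rand` is defined once, in 4.3.2: "Rand is an indicator variable for randomized treatment groups (1=aCRT ON, 0=aCRT OFF". No later section gives it another meaning.

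**The concern.** In 4.4.1 and 4.4.2 the text and the code specify different analyses. The SAP has a name for actual programming and uses it for the primary endpoint, but not for the two component endpoints. A programmer who followed the code would deliver a near-duplicate of the first sensitivity analysis under an as-treated label, and agreement between the two could be mistaken for robustness to crossover. For mortality, 4.4.1 itself says that ITT does not apply to the programming analysis, so the code contradicts the section it sits in.

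The output has readers. Table 2 in SAP 4.1.3 sends the sensitivity analyses of the primary endpoint, mortality and HF events to the DMC at each interim analysis, and SAP 4.2 asks that those three outcomes be weighed together.

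The primary-endpoint code raises a smaller, conditional question. A three-level variable outside CLASS receives one slope, and one slope cannot in general represent two contrasts.

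**Working it through.** The plan states no figure for these analyses, so there is none to reproduce. The check has three parts.

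**1. What the mortality and HF-event code estimates.** At each event time, every patient at risk contributes exactly one (start, stop) record. If the covariate is constant within a patient, each risk set holds the same values whether or not follow-up was split, so the Cox partial likelihood is unchanged. Splitting records therefore does nothing when the covariate is `rand`. In simulated trials, `rand` on split and on unsplit records gave the same coefficient every time (largest difference about 1e-13).

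**2. Size, as an illustration.** The inputs are the plan's assumptions for the primary composite:

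- hazard ratio 0.78 in confirmed LBBB; crossover 5% (ON) and 8% (OFF) at 2 years; loss to follow-up 5% at 2 years (SAP 4.3.8);
- control event-free rate 85% at 2 years, so the hazard is −ln(0.85)/2 = 0.0813 per year; 4 years' accrual plus 3.5 years' follow-up (protocol 11.3.4);
- 3500 × 0.90 = 3150 patients with confirmed LBBB.

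The assumptions added are exponential times, crossover at a constant rate unrelated to prognosis, no censoring at crossover, and no follow-up in Neither. Mean hazard ratios over 60 simulated trials:

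| Crossover at 2 years (ON / OFF) | `rand`, as coded | Actual programming |
|---|---|---|
| 5% / 8% (plan) | 0.821 | 0.787 |
| 15% / 20% (assumed) | 0.860 | 0.782 |

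The true value is 0.78; the gap to 0.787 is simulation noise. On the log scale at the planned rates, ln(0.821)/ln(0.787) = 0.197/0.240 = 0.82, so about 18% of the effect is lost. A hand approximation gives exp[(1 − 0.05 − 0.08) × ln 0.78] = exp(0.87 × −0.2485) = 0.81. It is cruder because it applies the 2-year crossover to the whole of follow-up.

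**3. The missing CLASS entry in 4.3.4.** If `aCRTprog` is a character variable, PHREG will not accept it outside CLASS, and the error is visible. If it is numeric, one slope forces log-hazard steps proportional to the code values. With no time in Neither this is harmless: the single slope gave 0.787, the same as the categorical fit. With some time in Neither, the implied ON versus OFF hazard ratio depends on the numeric codes and on the hazard in Neither. The documents give neither, so I tried three codings (OFF/ON/Neither = 0/1/2, 2/1/3 and 1/2/0) and a Neither hazard of 1 to 2 times OFF, at the planned crossover:

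| Moved to Neither by 2 years (assumed) | One numeric slope, range | Categorical fit, range |
|---|---|---|
| 0% | 0.787 | 0.787 |
| 1% | 0.75 to 0.86 | 0.77 to 0.78 |
| 2% | 0.73 to 0.93 | 0.79 |
| 5% | 0.68 to 1.08 | 0.78 |

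The error can go in either direction.

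**The case against.** The text of 4.4.1 and 4.4.2 states the intended analysis correctly, including the time-varying covariate, multiple records and a separate crossover dataset, so a careful programmer might well follow the text. Much SAP code is offered only as similar to what will be run, and some of it is plainly not run-ready (the R call in 4.4.2 has unbalanced parentheses). This makes a copying slip likely. It does not remove the conflict: the as-treated blocks in 4.4.1 and 4.4.2 carry no such qualifier, and nothing says that `rand` is to be overwritten with actual programming.

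Censoring is a stronger point. SAP 4.1.2.3 and 4.3.4 censor patients at major protocol violations, for example a permanent departure from the assigned mode caused by a system modification. Until such a patient is censored, `rand` and actual programming agree, so that crossover does not dilute a `rand` fit. This stands. How far it reaches is unclear, because 4.3.4 also keeps records after crossover, and 4.4.1 and 4.4.2 do not restate the rule. The simulation did not apply it. If every crossover were censored, `rand` would match actual programming apart from time in Neither.

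A reader might also infer that none of the three models can give an as-treated effect. The documents do not support that for the primary endpoint: the variable is the right one, and harm requires both numeric coding and follow-up in Neither. Nor may 0.82 versus 0.79 be read as the bias for mortality or HF events, because 0.78 is the design assumption for the composite.

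**Conclusion.** The mismatch in 4.4.1 and 4.4.2 is established from the SAP alone. Run as written, both analyses give a randomised-arm estimate in core-lab-confirmed LBBB patients, without site frailty and with a robust variance, and not an as-treated effect. This rests only on `rand` keeping its one defined meaning.

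The size for these endpoints is not known. With the composite's inputs and planned crossover it ranges from no difference, if all crossovers are censored and none go to Neither, to about 0.82 against 0.79, if none are censored. The error is towards the null when crossover is unrelated to prognosis. It would be larger with more crossover.

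The CLASS omission in 4.3.4 is a conditional fault, with a size that the documents do not determine.

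The consequence is confined to sensitivity analyses. The primary ITT test, the alpha spending, the Hommel procedure and the sample size do not depend on this code. It is still more than a clerical matter, because it changes a reported result.

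**What to change.** 1. In the second sensitivity model of SAP 4.4.1 and of 4.4.2, replace `rand` with `aCRTprog`.
2. In all three as-treated models (4.3.4, 4.4.1, 4.4.2), list the variable in CLASS with OFF as reference, for example `CLASS NYHA aCRTprog(ref='ACRT OFF') / PARAM=ref;`.
3. Pre-specify the ON versus OFF contrast as the reported result, for example with `HAZARDRATIO aCRTprog / DIFF=ref;`. With three levels, the overall test of `aCRTprog` has two degrees of freedom, so the p-value for treatment that 4.3.4 refers to needs to be tied to this contrast.
4. State in 4.4.1 and 4.4.2 whether the exclusion and censoring rules of 4.3.4 apply, so that it is clear which crossover time remains.

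The cost is a few lines of SAP text and code. The split-record datasets are already planned, so no new data are needed.

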4.4.2 Secondary Objective #2: Intervention for heart failure decompensation

The secondary objective #2 is to test the hypothesis that aCRT ON reduces the rate of intervention for heart failure decompensation compared to aCRT OFF. It is the other component of the two that comprise the primary endpoint.

Hypothesis

Per CIP, intervention for heart failure decompensation (HF event) is an event that requires “*invasive intervention (i.e. IV diuretics, ultrafiltration, or equivalent) or inpatient hospitalization*”. The terms “intervention for heart failure decompensation” and “HF event” are exchangeable also in the SAP.

Considering the presence of death as a competing risk, the cumulative incidence function (also called subdistribution function) of intervention for heart failure decompensation in the treatment arm, $F_T(t)$, and control arm, $F_C(t)$, are the proportion of patients that have had the first intervention for heart failure decompensation prior to time t .

In a competing risks setting, the effect of covariates can be modeled in two distinct manners^{14 15}. Covariates can be modeled as having a multiplicative effect on either (1) the cause-specific hazard (Cox regression), or (2) the derivative of the cumulative incidence function (Fine-Gray regression).

In the primary analysis, Cox regression will be used for competing risk analysis where the hazard of the event of interest is modeled and there is no simple connection between covariate effect from Cox model and cumulative incidence curves.

Let $h_T(t)$ and $h_C(t)$ be the associated hazard functions. Under the Cox regression model, $h_T(t) = HR \cdot h_C(t)$, where HR is the hazard ratio of treatment compared to control for HF event. The null and alternative hypotheses can be expressed as:

$$H_0 : HR = 1$$

$$H_A : HR \neq 1$$

Analysis Method

The crude cumulative incidence curves of intervention for heart failure decompensation will be displayed by treatment and NYHA class combinations using the SAS autocall macro %CUMINCID:

```
%cumincid(data=HFevent, time=TtoHFevent, status=HFeventCens,  
event=1, compete=2, censored=0, strata=randNYHA)
```

where TtoHFevent starts from the date of randomization and ends at the date that the first HF event occurs for those who experience the HF event, or the date of death for those who died before experiencing a HF event, or the date of last documented follow-up for those who are censored. HFeventCens = 0 when a subject did not experience a HF event or death and therefore was censored; HFeventCens = 1 when a subject experienced a HF event the first time since randomization; HFeventCens = 2 when a subject died without experiencing a HF event. The competing risk exists when HFeventCens = 2.

The hypothesis regarding the aCRT effect on HF event will be tested using a Cox proportional hazards regression model with a random site effect (frailty), stratified by NYHA class at enrollment. Section 4.3.2 has described this model in details. The analysis will be conducted using code similar to:

```
PROC PHREG DATA=HFevent;  
  CLASS NYHA site;  
  MODEL time*HFevent(0) = rand / TIES=efron;  
  STRATA NYHA;  
  RANDOM site/dist = gamma;  
RUN;
```

In these codes, HFevent = 1 if a subject experienced a HF event and HFevent = 0 otherwise; time to HF event starts from the date of randomization and ends at the date that the first HF event occurs for those who experienced at least one HF event, or the date of last documented follow-up or date of death for those who are censored. Date of last documented follow-up since randomization is the maximum value among the dates of randomization, randomization programming, any study scheduled follow-up visit, exit, adverse event onset, adverse event resolved, system modification, and healthcare utilization.

The model assumptions will be checked using the same methods that are described in detail in section 4.3.2 for the primary endpoint. That is, the assumption of proportional hazards between the treatment arms will be checked by testing the significance of treatment by time interaction term; and, the assumption of constant hazard ratio for treatment across NYHA classes will be checked by testing the significance of treatment by

NYHA class interaction and evaluating the hazard ratio for treatment within each NYHA class.

Missing Data

Non-informative censoring is assumed for lost to follow up in the analysis of intervention for heart failure decompensation

Secondary Competing Risk Analysis: Fine-Gray Regression

In addition to the Cox regression as the primary analysis for HF event, Fine-Gray regression will be conducted as a secondary competing risk analysis.

Let $h_T(t)$ and $h_C(t)$ be the subdistribution hazard of $F_T(t)$ and $F_C(t)$, respectively. Under the Fine-Gray model¹⁶ that assumes proportional subdistribution hazards, $h_T(t) = \text{SHR} \cdot h_C(t)$, where SHR is the subdistribution hazard ratio of treatment compared to control for intervention for heart failure decompensation. The null and alternative hypotheses are:

$$H_0 : \text{SHR} = 1$$

$$H_A : \text{SHR} \neq 1$$

The hypothesis regarding the aCRT effect on incidence of intervention for heart failure decompensation will be tested using a stratified Fine-Gray model where random center effect is not considered. The code will be something like below:

```
data Risk;
  NYHAc=2; rand=1; output;
  NYHAc=2; rand=0; output;
  NYHAc=3; rand=1; output;
  NYHAc=3; rand=0; output;
  NYHAc=4; rand=1; output;
  NYHAc=4; rand=0; output;
run;
proc phreg data=HFevent plots(overlay=stratum)=cif ;
  class NYHAc rand;
  model TtoHFevent*HFeventCens(0)= rand / eventcode=1;
  strata NYHAc;
  hazardratio 'Pairwise' rand / diff=pairwise;
  baseline covariates=Risk out=out1 cif=_all_ / rowid=rand;
run;
```

where EVENTCODE=1 indicates the event of interest is intervention for heart failure decompensation (i.e. HFeventCens = 1). HAZARDRATIO statement requests the subdistribution hazard ratio and its 95% confidence interval of treatment. BASELINE statement with COVARIATES= option display the cumulative incidence curves of aCRT ON and aCRT OFF for each NYHA class.

The following model assumption will be checked.

1. Constant subdistribution hazard ratios of treatment across NYHA classes: instead of stratified Fine-Gray, NYHA class will be regarded as a covariate in a Fine-Gray model along with the interaction between treatment and NYHA class. If the interaction is not

significant, this assumption would be valid. Otherwise, NYHA class will be regarded as a covariate instead of a stratification factor in the Fine-Gray model.

```
proc phreg data=HFevent;  
  class NYHAc rand;  
  model TtoHFevent*HFeventCens(0)= rand|NYHAc / eventcode=1;  
  hazardratio 'Pairwise' rand / diff=pairwise;  
run;
```

In addition, an R package of 'crrSC' which performs competing risk analysis for stratified data or clustered data may be considered.

Sensitivity Analyses: LBBB Determination and aCRT Programming

The first sensitivity analysis is to verify the effect of aCRT treatment on HF event among the true LBBB patients. The same model used in the primary analysis will be used in this sensitivity analysis. The only difference is that patients included in the sensitivity analysis must have their LBBB confirmed by ECG Core Lab.

```
PROC PHREG DATA=HFevent_LBBB;  
  CLASS NYHA site;  
  MODEL time*HFevent(0) = rand / TIES=efron;  
  STRATA NYHA;  
  RANDOM site/dist = gamma;  
RUN;
```

The second sensitivity analysis is to check the effect of aCRT on HF event based on the actual aCRT programming, given that patients' LBBB has been confirmed by the ECG Core Lab. Again, actual aCRT programming will be a time-varying covariate, meaning patients whose actual aCRT programming change over time will have multiple records in the input dataset. This will be performed using the COVSANDWICH option in the SAS PHREG procedure, and random site effect will not be considered in this sensitivity analysis.

```
PROC PHREG DATA=HFevent_LBBBCross COVSANDWICH (AGGREGATE);  
  ID pt;  
  CLASS NYHA site pt;  
  MODEL (start,stop)*HFevent(0) = rand / TIES=efron;  
  STRATA NYHA;  
RUN;
```

Subgroup Analysis: Interaction with Treatment

The same subgroups that are considered for the primary endpoint and 1st secondary endpoint will be considered for intervention for heart failure decompensation. These include:

- Geography: US/Canada vs. International
- Age
- Gender: Males vs. Females
- QRS duration: ≤150ms vs. >150ms
- AV conduction time: median as cutoff
- LBBB: Core Lab confirmed vs. Core Lab not confirmed

- NYHA class (in different model where NYHA class is a covariate not a stratification factor)
- HF etiology
- Renal dysfunction
- Diabetes

The effects of treatment by subgroup interaction on intervention for heart failure decompensation will be evaluated using codes similar to:

```
PROC PHREG DATA=HFevent_Subgroup;  
  CLASS NYHA site Subgroup;  
  MODEL time*HFevent(0) = rand subgroup rand*subgroup / TIES=efron;  
  STRATA NYHA;  
  RANDOM site/dist = gamma;  
RUN;
```

Ancillary Analysis: Covariate Adjustment

The process of ancillary analysis for intervention for heart failure decompensation follows similar rules as those for the primary endpoint. NYHA class at enrollment will be regarded as a covariate instead of a stratification factor in this ancillary analysis. Thus, the entire process will be based on frailty models. In the beginning the effect of each subject characteristic on intervention for heart failure decompensation will be tested in a univariate frailty model using codes similar to the below:

```
PROC PHREG DATA= HFevent;  
  CLASS site SubjCha; * CLASS only if SubjCha is categorical;  
  MODEL time* HFevent(0) = SubjCha / TIES=efron;  
  RANDOM site/dist = gamma;  
RUN;
```

After that, the final multivariate Cox regression model will be determined from the full model using backwards selection. Note the backwards selection will be performed manually because the SAS PHREG procedure ignores the SELECTION option for the frailty model analysis.

Analysis of Recurrent HF Events

In this analysis, the incidence of intervention for heart failure decompensation will be summarized and compared between the two treatment arms using a multistate Markov model. This model is also referred to as a stratified Andersen-Gill model.¹⁷ This model was recommended because it allows a flexible modelling strategy that incorporates important features in the analysis of intervention for HFdecompensation and death and in the meantime extends relevant characteristics of other models for analysis of recurrent events.¹⁸ Stratification of NYHA class and random center effect will not be considered in this analysis.

The multi-state model stratifies a Cox model by transition states as follows.

$$\alpha_k(t | X) = \alpha_{k_0}(t) \exp(X' \beta)$$

for covariates X, time t and transition states from k = 1, ..., K.

These transition states include first intervention for HF decompensation, second intervention for HF decompensation, etc., death, death after first intervention of HF decompensation, death after second intervention for HF decompensation, etc.

The dataset should be arranged similar to:

PTID	Time1	Time2	Transition	Status	trtGroup
M0000001	0	60	R->H1	0	1
M0000001	0	60	R->D	0	1
M0000002	0	14.2	R->H1	1	2
M0000002	0	14.2	R->D	0	2
M0000002	14.2	60	H1->H2	0	2
M0000002	14.2	60	H1->D	0	2
M0000003	0	24.7	R->H1	0	2
M0000003	0	24.7	R->D	1	2
M0000004	0	38	R->H1	1	1
M0000004	0	38	R->D	0	1
M0000004	38	48.5	H1->H2	0	1
M0000004	38	48.5	H1->D	0	1

In this dataset (which will be referred to as mmsurvdata),

- The following definitions apply:
 - Time1 and Time2 are the start and end time of a period at risk for an event, which can be either a HF endpoint or a censoring event
 - The events being modeled are Randomization (R), first intervention for HF decompensation (H1), second intervention for HF decompensation (H2) and Death (D)
 - A subject from R can transition to H1 (R->H1) or D (R->D) and a subject from H1 can transition to H2 (H1->H2) or D (H1->D)
 - Status indicates whether a possible transition occurred (Status=1) or no longer at risk to present transition (Status=0)
 - trtGroup indicates whether the subject is aCRT ON (trtGroup =1) or aCRT OFF (trtGroup =2)
- The subject histories in the example dataset shown above were as follows:
 - Subject M0000001 made it 60 months with no intervention for HF decompensation or death
 - Subject M0000002 had an intervention for HF decompensation at 14.2 months and made it the remainder of the 60-month follow-up with no additional intervention for HF decompensation nor death
 - Subject M0000003 died at 24.7 months without a prior HF event
 - Subject M0000004 had a HF event at 38 months and had accrued 48.5 total months of follow-up

The definition above accounts for up to two HF events. For the actual analysis, the breadth of transition events will be dependent on the data. The value N for

H[N-1]->H[N]

where N is the maximal number of HF events modeled, will require that an adequate number of subjects experience at least N HF events. The definition of adequate will be guided by the data, but will ultimately be left to the discretion of the analysts.

R code for implementing the multistate Markov model will be similar to:

```
> library(survival)
> fit1 <- coxph(Surv(time1, time2), status) ~ factor(trtGroup) + cluster(pt) +
strata(transition), data= mmsurvdata)
> print(cox.zph(fit1))
```

Determination of Patients/Data for Analysis

Again, the primary, subgroup and ancillary analysis for intervention for HF decompensation will follow the ITT principle and include all randomized patients; while sensitivity analysis will only include randomized patients with ECG Core Lab confirmed LBBB.

